8.5.2.3 Assessment of Mucosal Responses

Nasal lining fluid samples will be collected to evaluate PK or SARS-CoV-2 antigen-specific antibody responses in nasal secretions. Samples will also be collected at Illness Visits. Nasal lining fluid samples will be collected, when test supplies are available, by synthetic absorptive matrix sampling as outlined in the Laboratory Manual. AZD7442 nasal concentrations may be assessed using an appropriately qualified bioanalytical assay.

8.5.2.4 Assessment of Cell-mediated Immune Responses

Cell-mediated immune responses (ie, B-cell and T-cell responses) will be assessed by characterizing PBMCs isolated from selected sites using methods that may include T-cell ELISpot assays to SARS-CoV2 antigens, flow cytometry after intracellular cytokine staining, single-cell RNA sequencing, B-cell and T-cell receptor sequencing, and other methodology as determined by the Sponsor, as technical and/or operational feasibility allows.

8.5.2.5 Additional Serum Immunogenicity

Additional serum samples will be collected for exploratory immunogenicity evaluation. Serologic assessment to seasonal coronavirus antigens may also be assessed quantitatively using a qualified multiplexed meso scale discovery (MSD) immunoassay. Exploratory sera samples may be utilized to investigate additional humoral and cellular immune responses, as well as potential correlates of protection as determined by the Sponsor based upon emerging safety, efficacy, and immunogenicity data.

8.5.3 Pharmacodynamics

8.5.3.1 SARS-CoV-2 Neutralizing Antibody Assessments

Serum samples to measure SARS-CoV-2 nAb levels will be collected from participants according to the time points specified in the SoA (see Section 1.3). Authorized laboratories may measure nAbs to SARS-CoV-2 using validated live virus neutralization assays or pseudo-neutralization assays.

For storage, re-use, and destruction of PD samples, see Section 8.5 and Appendix C.

8.6 Human Biological Sample Biomarkers

8.6.1 Collection of Mandatory Samples for Biomarker Analysis

By consenting to participate in the study the participant consents to the mandatory research components of the study.

Samples for biomarker research are required and will be collected from participants, as specified in the SoAs (see Section 1.3). Nasopharyngeal swabs will be collected for virologic assessments. These biomarker measurements will support understanding of potential correlates of protection, duration of immune responses, and correlations between PD and immunogenicity. Details for sample collection, processing, and testing will be provided in the Laboratory Manual.

Any results from such analyses may be reported separately from the CSR.

8.6.1.1 Virologic Assessments

Nasopharyngeal swabs will be assessed by authorized RT-PCR assays for the detection of SARS-CoV-2 by local and central laboratories according to the time points specified in the SoA (Section 1.3). Instructions for obtaining and processing NP swab samples are provided in the Laboratory Manual.

The full-length S gene (AA 1-1274) from SARS-CoV-2-positive nasal samples may be amplified using a standard, single tube population-based RT-PCR method and sequenced by next-generation sequencing (NGS) at Illness Visits (Table 4). Amino acid variation across the full-length S protein sequence may be determined and reported separately from the CSR.

Amino acid changes identified by genotypic analyses of the S trimer protein ectodomain (AA 20-1213) can be evaluated by either a spike trimer binding affinity assay and/or a recombinant SARS-CoV-2 Spike-pseudovirus neutralization assay. Additional details on clinical virology analyses, including molecular surveillance of the S protein in global circulation will be provided in the Virology Analysis Plan.

Local and central assessments should be collected per the SoA (Section 1.3); where both local and central assessments are listed both are required and should be collected. Additionally, a validated multiplexed respiratory panel may be utilized to assess for the presence of other respiratory pathogens in NP swabs in a central laboratory operated on behalf of the Sponsor at Illness Visits.

8.6.2 Other Study-Related Biomarker Research

Already collected samples may be analyzed for different biomarkers thought to play a role in COVID-19 severity or outcomes, including, but not limited to, serum, plasma or mucosal cytokines, quantification of RNA, micro-RNA, and/or non-coding RNA, using quantitative RT-PCR, microarray, sequencing, or other technology in blood, PBMCs, or mucosal specimens to evaluate their association with observed clinical responses to AZD7442.

For storage, re-use, and destruction of biomarker samples see Section 8.5.

8.7 Optional Genomics Initiative Sample

Optional Genomics Initiative research is not applicable in this study.

8.8 Medical Resource Utilization and Health Economics

Medical resource utilization and health economics parameters are not collected or evaluated in this study.

9 STATISTICAL CONSIDERATIONS

9.1 Statistical Hypotheses

The primary objective of the study is to assess the safety and tolerability of AZD7442. No statistical hypotheses will be tested.

9.2 Sample Size Determination

Approximately 200 participants will be randomized to study intervention: 100 participants to Arm A (AZD7442 600 mg IM on Day 1 then 300 mg IM Q3M for 12 months) and 100 participants to Arm B (AZD7442 1200 mg IV on Day 1 then 600 mg IM Q6M for 12 months).

If the true AE rate is 3%, the probability of observing at least one AE in 100 participants is 95%. The number of participants in the study would also allow for assessment of immunogenicity based on ADA prevalence observed in PROVENT (D8850C00002; NCT04625725).

9.3 Populations for Analyses

The following populations are defined in [Table 10](#).

Table 10 Populations for Analysis

Population/Analysis set	Description
Enrolled	All participants who sign the ICF.
Full analysis set	All randomized participants who receive at least one dose of IMP. Participants will be assigned according to their randomized treatment according to the intent-to-treat principle.
Safety analysis set	All participants who have received at least one dose of IMP. Participants will be assigned in this analysis set by the arm of treatment they actually received.
PK analysis set	All participants in the safety analysis set who received AZD7442 and who had at least one quantifiable serum PK observation post dose will be included in the PK analysis dataset.
ADA evaluable analysis set	All participants in the safety analysis set who have a non-missing baseline AZD7442 ADA result and at least one non-missing post-baseline AZD7442 ADA result.
nAb evaluable analysis set	All participants in the safety analysis set from whom blood samples are assumed not to be affected by factors such as protocol violations, and who had at least one quantifiable serum observation post dose. At any time during the study, participants will be excluded from this analysis set at the point at which they receive an alternative COVID-19 mAb.

ADA, antidrug antibody; COVID-19, coronavirus disease 2019; ICF, informed consent form; IMP, investigational medicinal product; nAb, neutralizing antibody; PK, pharmacokinetic.

9.4 Statistical Analyses

Results will generally be summarized by treatment arm using descriptive statistics. Categorical variables will be summarized using frequency and percentages, where the denominator for calculation is the underlying analysis set population, unless otherwise stated. Continuous variables will be summarized with descriptive statistics of number of available observations, mean, standard deviation, median, minimum and maximum, and quartiles where more appropriate.

The final data readout will occur once all participants have completed the follow-up period (at Month 24) or withdrawn due to premature termination of the study.

9.4.1 Primary Endpoints

9.4.1.1 Safety

The safety of AZD7442 will primarily be assessed by the incidence and exposure adjusted incidence of AEs, SAEs, and AESIs.

Adverse event severity will be graded according to [Appendix B](#) and coded using the most recent version of the Medical Dictionary for Regulatory Activities. Adverse events will be presented by system organ class and preferred term. Summaries will include the number and percentage of participants reporting at least one event, number of events, and will include exposure adjusted rates. An overview of AEs will be presented for each group, including the number and percentage of participants with any AE and SAEs. Summaries will present the relationship to IMP as assessed by the Investigator, maximum intensity, seriousness, and death.

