- Arm A: AZD7442 600 mg IM on Day 1 followed by 300 mg IM Q3M for 12 months (ie, Days 92, 183, 274, and 365)

- Arm B: AZD7442 1200 mg IV on Day 1 followed by 600 mg IM Q6M for 12 months (ie, Days 183 and 365)

The total duration of the study for a participant is 105 weeks (approximately 24 months) for both arms which includes the screening period (up to one week), the treatment period (15 months), and the follow-up period (9 months).

Data Safety Monitoring Board

An independent Data Safety Monitoring Board will provide oversight, to ensure safe and ethical conduct of the study.

Cardiovascular Event Adjudication Committee

An independent cardiovascular (CV) Event Adjudication Committee will provide an independent, external, systematic, and unbiased assessment of de-identified blinded data to systematically evaluate CV events.

Statistical Methods

No statistical hypotheses will be tested. Results will generally be summarized by treatment arm using descriptive statistics: frequency and percentages for categorical variables; number of available observations, mean, standard deviation, median, minimum, and maximum, and quartiles where more appropriate for continuous variables.

The final data readout will occur once all participants have completed the follow-up period (at Month 24) or withdrawn due to premature termination of the study.

Primary Endpoints

- The safety and tolerability of AZD7442 will primarily be assessed by the incidence and exposure adjusted incidence of adverse events (AEs), serious adverse events (SAEs), and adverse events of special interest (AESIs).
- The incidence of antidrug antibodies (ADA) to AZD7442 will be assessed and summarized by number and percentage of participants who are ADA positive. The ADA titer will be summarized with descriptive statistics.

Secondary Endpoints

- Individual AZD7442 (tixagevimab and cilgavimab) serum concentration data will be listed and tabulated, along with descriptive statistics. Appropriate PK parameters may be calculated.
- Descriptive statistics for geometric mean titers (GMTs) and geometric mean fold rise (GMFR) in severe acute respiratory coronavirus-2 neutralizing antibodies will include number of participants, geometric mean, geometric standard deviation, 95% confidence interval, minimum, and maximum.

Sample Size

Approximately 200 participants will be randomized to one of 2 AZD7442 dosing regimens: 100 participants to Arm A and 100 participants to Arm B.

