1.3 Schedule of Activities

[Table 1](#) summarizes the SoA for the screening and treatment period for Arm A (AZD7442 Q3M).

[Table 2](#) summarizes the SoA for the screening and treatment period for Arm B (AZD7442 Q6M).

[Table 3](#) summarizes the SoA for the follow-up period for Arm A and Arm B.

[Table 4](#) summarizes the assessments to be conducted when Illness Visits are initiated for participants who are suspected to have COVID-19.

Participants who permanently discontinue IMP administration due to the premature termination of the study will remain in the study to complete visits/assessments (except those related to monitoring of IMP administration) for at least 6 months after their final dose of AZD7442.

- If participants receive their last study drug administration on Day 183 visit, they will complete Day 190, Day 212, and Day 274 (no dosing) visits, followed by an Early Discontinuation visit in place of the Day 365 visit.
- If participants receive their last study drug administration on Day 274 visit, they will complete Day 281, and Day 365 (no dosing) visits, followed by an Early Discontinuation visit in place of the Day 456 visit.
- If participants have already completed visit/assessments up to 6 months after the last IMP administration (i.e. Day 365), the early discontinuation visit will be scheduled as early as possible. However, if early discontinuation scheduling is within one month of last completed in person visit and required samples were collected per protocol, then no additional sample collection is required (with the exception of a urine pregnancy test for WOCBP, and if positive or indeterminant, serum pregnancy will be collected).
- If participants are completing an illness visit series, they will be followed until completion or until the Early Discontinuation visit.

Table 1 Schedule of Activities: Treatment Period – Arm A (AZD7442 Q3M)

Period	Screen ^a	Treatment (Days 1-456)													EoT	For details, see Section
Day (* = IMP dosing day)	-7 to 1	1*	8	29	92*	99	121	183*	190	212	274*	281	365*	372	456	
Week (Month)	-	-	1	4	13 (3M)	14	17 (4M)	26 (6M)	27	30 (7M)	39 (9M)	40	52 (12M)	53	65 (15M)	
Window (days)	-	-	± 3	± 5	± 7	± 3	± 5	± 7	± 3	± 5	± 7	± 3	± 7	± 3	± 15	
P = In-Person Visit RTM = Remote TM Visit ^m	P	P	RTM/ P ^m	P	P	RTM/ P ^m	P	P	RTM/ P ^m	P	P	RTM/ P ^m	P	RTM/ P ^m	P	
Procedure																
Informed consent	X															5.1
Informed assent for pediatric participants	X															5.1

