4.2 Scientific Rationale for Study Design

This is a Phase II randomized, open-label study with 2 treatment arms. Randomization will minimize potential bias in dose selection.

The study will enroll adults and pediatric individuals (≥ 12 years of age weighing at least 40 kg) who are moderate to severely immunocompromised due to an underlying disease or are taking immunosuppressive medications and therefore unable to mount an adequate immune response to COVID-19 vaccine.

The primary objective of the study is to assess safety and immunogenicity (ADA) of AZD7442 dose regimens (600 mg IM followed by 300 mg IM Q3M and 1200 mg IV followed by 600 mg IM Q6M) in this population. The repeat dosing treatment regimens with a duration of 12 months will allow for collection of safety endpoints (AEs, SAEs, and AESIs) and ADA data after repeat dosing with AZD7442. A follow-up of 12 months after the participant's last dose will provide additional safety and immunogenicity data on AZD7442.

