Summary of AEs and SAEs post the first dose of IMP will be broken down further by maximum severity. Severity, adapted from the CTCAE v5.0 (see Appendix A 2), will be classified as Grade 1 (mild), Grade 2 (moderate), Grade 3 (severe), Grade 4 (life-threatening or disabling), and Grade 5 (death) by using grading for AEs. Severity for AEs will be collected on “Adverse Events” form of eCRF. Should a participant experience multiple events within a SOC or PT, only the participant’s worst severity grade will be counted for that SOC or PT.

Relationship to IMP/Study Procedure

Relationship to IMP/ study procedure, as indicated by the Investigator, will be classified as not related or related. Should a participant experience multiple events within a SOC or PT, the participant will be counted as related for that SOC or PT if the event is related to either IMP or study procedure.

Exposure adjusted rate

Exposure adjusted rate is calculated as number of participants with AEs in categories divided by total participant-year follow-up for each treatment group. Participant years is determined by summing the total number of follow-up days of each participant, and then dividing by 365.25. The exposure period is calculated from time of first dose to end of study, or the current data cut-off, whichever is earlier.

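### The AE tables pool all follow-up from the first dose, so they cannot show how often AEs occur after repeat dosing, which is what the trial set out to learn

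*Protocol*

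**What the plan says.** Protocol 9.4.1.1 sets the content of the AE summaries: "Summaries will include the number and percentage of participants reporting at least one event, number of events, and will include exposure adjusted rates". SAP 4.3.2.1 defines the rate: "Exposure adjusted rate is calculated as number of participants with AEs in categories divided by total participant-year follow-up for each treatment group". The person-time is a single block: "The exposure period is calculated from time of first dose to end of study, or the current data cut-off, whichever is earlier".

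SAP 4.3.2.2 applies this to AEs, SAEs, AESIs and Grade 3 or higher AEs. A participant with several events in a category is counted once. The SAP section also leaves out the number of events that the protocol promises. It mentions a study period when describing maximum intensity but defines none. The analysis set, in Protocol 9.3, is "All participants who have received at least one dose of IMP", so participants who were never re-dosed are included.

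On purpose, Protocol 2.1 presents the trial as a study of repeat dosing regimens, and 4.2 says: "The repeat dosing treatment regimens with a duration of 12 months will allow for collection of safety endpoints". The first repeat dose falls on Day 92 in Arm A and Day 183 in Arm B (Synopsis, Intervention Groups and Duration). Protocol 1.3 gives the visit paths after termination. The one beginning "If participants receive their last study drug administration on Day 183 visit" ends with an Early Discontinuation visit in place of Day 365. A last dose on Day 274, which only Arm A has, leads to a final visit in place of Day 456.

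**The concern.** A trial of repeat dosing should be able to say whether AEs become more or less frequent on re-dosing. Followed as written, its primary AE tables cannot. Time and events after the first (loading) dose are merged with those after later doses, and an AE that recurs after re-dosing adds nothing to a count of participants.

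The protocol itself gives reason to expect change, in both directions. Section 2.3.1 says anaphylaxis usually follows a later exposure, whereas infusion-related reactions are less common on later exposures. Both are AESIs.

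The mixture also differs between arms, because Arm B waits twice as long for its second dose. Arm B's first dose is intravenous, so no reaction to an IM injection can arise there before Day 183, yet that time is in the denominator.

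**Working it through.** **The plan's own AE figure.** Protocol 9.2 gives a 95% chance of seeing at least one AE among 100 participants if the true rate is 3%. Check: 1 − 0.97^100 = 0.952, which agrees. The figure counts everyone from the first dose. If, as an assumption, only 80 were re-dosed, the chance for an AE with the same 3% rate after re-dosing would be 1 − 0.97^80 = 0.913.

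**Share of follow-up before any repeat dose.** Days before the second dose: 92 − 1 = 91 in Arm A and 183 − 1 = 182 in Arm B. Share = days before second dose ÷ last day of follow-up.

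| Follow-up ends | Arm A | Arm B |
|---|---|---|
| Day 365 (last dose Day 183) | 91/365 = 24.9% | 182/365 = 49.9% |
| Day 456 (last dose Day 274) | 91/456 = 20.0% | no Day 274 dose |
| Day 729 (original design) | 91/729 = 12.5% | 182/729 = 25.0% |

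The actual mix of last doses is not in the documents. On the two listed termination paths Arm A lies between 20.0% and 24.9%.

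**Possible effect on the pooled event rate.** Assume the same event rate in both arms before re-dosing, multiplied afterwards by the same factor r. Pooled rate relative to the first-dose rate = share + (1 − share) × r.

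| r | Arm A, Day 365 | Arm B, Day 365 | A/B at Day 365 | A/B at Day 729 |
|---|---|---|---|---|
| 1 | 1.00 | 1.00 | 1.00 | 1.00 |
| 1.5 | 1.38 | 1.25 | 1.10 | 1.05 |
| 2 | 1.75 | 1.50 | 1.17 | 1.07 |
| 3 | 2.50 | 2.00 | 1.25 | 1.10 |

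The values of r are assumptions. The documents give none, and r could be below 1.

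**The SAP's own rate.** The SAP counts participants, not events. With constant hazards and follow-up to Day 365 in both arms, the proportion with an event is 1 − exp(−H). Here H = h × (d + r × (365 − d))/365.25, h is the first-dose hazard per year and d is 91 or 182. Person-time is equal in the arms, so the rate ratio equals the ratio of proportions.

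| First-dose hazard per year | r = 1.5 | r = 2 | r = 3 |
|---|---|---|---|
| 0.03 | 1.10 | 1.16 | 1.24 |
| 1 | 1.05 | 1.06 | 1.06 |
| 2 | 1.02 | 1.02 | 1.01 |

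For rare events the two measures agree. For common AEs the participant count saturates and the arms hardly differ: at hazard 1 and r = 3, the proportions are 91.8% and 86.5%. In that setting a threefold rise on re-dosing would leave little trace in the planned between-arm figure.

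**The case against.** The strongest reply is that the arms are randomised regimens, each including its loading dose, and that person-time starts at the first dose in both. If re-dosing raised AE rates, the arm re-dosed earlier really would have more AEs over the year. A ratio of 1.10 to 1.25 would then be a true regimen difference, not an artefact. No hypothesis is tested. All of this stands. A reader might infer that the pooled tables compare the arms unfairly or produce a spurious difference. The documents do not support that. What would be wrong is to read the pooled contrast as one between repeat doses, and neither document proposes that reading.

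A reader might also infer that nothing about repeat dosing will be shown. That goes too far. Vital signs are summarised before and after each dose, laboratory results and ADA by visit, and AEs and doses are listed. The gap is in the AE tables.

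A third reply is that a table by dose does not isolate repeat dosing. Protocol 2.2 gives a mean half-life of about 90 days in healthy adults. At Day 92 about 0.5^(91/90) = 50% of the first dose would remain, and at Day 183 about 0.5^(182/90) = 25%. Dose number is also tied to dose level, to route in Arm B, to calendar time and to selection of those who are re-dosed. This stands as well. It limits how the table may be interpreted, but it is not a reason to omit it.

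**Conclusion.** The point holds as a gap in presentation, not as a bias in the primary safety analysis. The planned AE tables answer the whole-regimen question and cannot answer the repeat-dose one.

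The shares of 25% and 50% rest on a last dose on Day 183 and follow-up to Day 365, which matches the 12 months of data the sponsor expects after termination. They should not be quoted without that condition. The effect on the pooled figures cannot be known from the documents. The ratios of 1.10 to 1.25 are event-rate illustrations under an assumed common rise of 1.5 to 3-fold; they become 1.00 with no rise and shrink towards 1 on the SAP's measure for common AEs. The missing table does not depend on those assumptions, nor does Arm B's pre-Day 183 time in the denominator for injection-site reactions.

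**What to change.** Keep the pooled tables. Add to SAP 4.3.2.2, with a matching sentence in Protocol 9.4.1.1, a descriptive table of AEs, SAEs, AESIs and Grade 3 or higher AEs by interval:

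- first dose to before the second dose;
- second dose onward, split by dose number where counts allow.

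Assign each AE by start date to the latest preceding dose. For each interval give participants entering it, participants with an event, number of events and person-years. Show injection-site reactions over IM-exposed participants and time only. Base any statement on repeat-dose safety on these rows, and say in the text that the pooled between-arm figure is a regimen contrast.

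The cost is some wording in both documents and one table set. Dose dates (Protocol 6.4) and AE start dates (8.3.2) are already recorded, so no new data are needed. The drawbacks are small counts after later doses and the confounding set out above, so the table must be labelled descriptive.
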